## 4.3 Enrollment onto the study

During the official enrollment period, for participants who are considered eligible for the study based on the initial questionnaire and follow-up conversation, the call center at the CRO will contact the participant. The participant will be asked to confirm their identity against the details provided in the online screener by providing their full legal name and date of birth. During this call, the study member will share additional information about the study, including a copy of the Informed Consent Form (ICF) via email and / or text message. The participant will also be asked whether or not they have had sufficient time to read, understand and ask questions about this study and ICF. The participant may take as much time as they would like to read, understand and ask questions about this study and ICF. Additionally, the participant may ask the study member to read the entire ICF over the phone. During enrollment, a study member will discuss the risks and benefits of the study, answer any questions the patient may have about participation, and collect additional details for eligibility.

If the participant decides to enroll onto the study, the participant will consent to enrollment using a secure online signature platform. In the online signature platform, the participant will be asked to sign the informed consent form (ICF) as well as sign required medical data release forms for releasing colonoscopy and histopathology results. A participant will be considered enrolled after understanding and signing the ICF.

During enrollment, the subject will be assigned a unique subject identifier number that will permit deidentification of the subject through the entirety of the study. Whether the participant chooses to provide consent to participate or declines to participate, the participant's response will be recorded and saved for study documentation in the Trial Master File and subject to the Data Management Plan.

# 4.4 Confirming a Colonoscopy

This study requires eligible participants to have a routine, standard-of-care colonoscopy. After a participant has been enrolled onto the study, the study member will assist the participant to schedule a colonoscopy. Once the call

		ccc	DV	INC.
CIFI	urc)	SUL	IPY.	HIMU
			,, ,,	

**Document Number: VAL-PRT-0041** 

center confirms the subject has a colonoscopy scheduled, the study member will record this information and provide updates to the participant, as needed. The care coordinators at the call center will provide reminders to participants via email, text, or outbound phone calls to attend their appointments and to follow their physician's instructions in order to help them maintain eligibility.

#### 5. Protocol Plan

#### **5.1 Sample Collection**

Once a participant has signed the ICF and scheduled a colonoscopy procedure, the study members at the CRO will issue the mt-sRNA test collection kit to the patient's residence. This collection kit will contain all materials necessary to collect a viable sample for processing. The Collection Kit will contain the following:

- Collection Kit Instructions For Use: Instructions for using the Collection Kit
- Attestation Form: Form to attest that the sample was derived from the correct participant.
- **iFOB Sampling Bottle**: OC-Auto Micro 80 iFOB Test (iFOB) Sampling Bottle
- iFOB Sampling Bottle Ziplock Bag: plastic bag to prevent stool leakage during shipping
- Stabilization Liquid: preservative buffer for stool storage during shipping
- Sample Container: plastic bucket for stool sample collection
- Container Lid: plastic top for stool sample collection
- Sample Labels: stickers for the collection kit components
- Seat Bracket: plastic tool to hold Sample Container for stool sample collection
- Shipping Box: cardboard container for return of stool sample
- Prepaid Shipping Label: barcode for return shipping of stool sample
- Label Package Seals: stickers for closing the mailing container
- Inner Ziplock Bag (Bag #1): plastic bag to prevent stool leakage during shipping
- Outer Ziploc Bag (Bag #2): plastic bag to prevent stool leakage during shipping
- Absorbance Sheet: sheet to absorb liquid if leaked outside of the container

The specimen must be collected prior to initiation of bowel preparation for the colonoscopy. Collection materials will be labeled with the patient's unique identifier so that the sample can be linked to the individual. The collection materials will also contain an attestation form so the patient can confirm the origin of the sample. Detailed instructions will be provided to the participant in the form of an Instructions for Use (IFU) booklet. Per the IFU, stool samples and iFOBT swabs will be collected by the participant at the participant's convenience, so long as the collection was performed prior to the colonoscopy preparation and the colonoscopy procedure.

#### 5.2 Collection Kit: Obtaining a stool sample and iFOBT swab

Once the collection kit is sent to the participant's house, the subject will be instructed to follow the collection kit IFU booklet. The collection kit IFU will provide step-by-step instructions with associated images for how to complete sample collection. Briefly, these instructions are provided below:

- 1. The patient will open the collection kit by ripping the perforated edge and opening the flaps of the box,
- 2. The patient will unpack the kit by placing the contents of the kit onto a surface near the stool collection location. This includes:
  - a. Removing the sample container / lid from the box,
  - b. Removing the seat bracket from the box,

Title: CRC-PREVENT Clinical Validation Protocol

**Document Number: VAL-PRT-0041** 

- c. Removing the iFOBT tube from the box,
- d. Removing the Stabilization Buffer from the box,
- 3. The patient will collect the stool sample by placing the bracket onto the toilet seat and setting the sample container into the seat bracket. The patient will then replace the toilet seat and sit on the toilet. Finally the user will produce a stool sample into the sample container.
- 4. The patient will use the iFOBT Sampling Bottle to swab the stool sample. This requires:
  - a. Unscrewing the iFOBT Sampling Bottle tube cap,
  - b. Swabbing the stool sample in a cross-hatch motion using the swab on the iFOBT tube cap,
  - c. Replacing the iFOBT tube cap into the iFOBT Sampling Bottle with the iFOBT buffer.
- 5. The patient will stabilize the stool sample by pouring the Stabilization Liquid into the stool sample container.
- 6. The patient will secure the sample by tightly sealing the sample container. This requires:
  - a. Removing the sample container from the toilet and plating onto a steady surface,
  - b. Placing the container lid onto the sample container,
  - c. Pressing firmly onto all sides of the container lid until no more audible clicks can be heard,
  - d. Rotating the lid to ensure proper seal.
- 7. The patient will be instructed to record sample information on the iFOBT Sampling Bottle and the Attestation Form.
- 8. The patient will place the components into the appropriate bags and all bags will be tightly sealed:
  - a. iFOBT Sampling Bottle will be placed into small Ziplock Bag
  - b. Sealed sample container will be placed into Ziplock Bag #1
  - c. Ziplock Bag #1 will be placed into Ziplock Bag #2
- 9. All components will be placed into the shipping box. Components include:
  - a. iFOBT Sampling Bottle in Ziplock bag,
  - b. Sample container in two Ziplock bags,
  - c. Attestation Form
  - d. Empty Stabilization Buffer
- 10. The patient will be instructed on how to ship the sample back to Geneoscopy's Laboratories. This includes sealing the collection box and returning it to the FedEx drop off location or ordering a courier to pick up the box from the patient's residence.

If the subject encounters any issues during sample production, the participant will be instructed to call the CRO call center. If a collection kit is defective, the participant will be instructed to ship the collection kit back to Geneoscopy's centralized laboratory and a subsequent collection kit will be issued to the participant. The same rules should apply in the event that a stool collection kit is misplaced, lost, or never received.

Once the sample collection is complete, per the IFU, the participant is instructed to schedule a pickup or drop the collection kit off at a courier location. The return label on the collection kit will send the kit to Geneoscopy's centralized laboratory. The shipment and arrival to Geneoscopy will be tracked by the courier and will be recorded by the CRO. Once the sample arrives at Geneoscopy's laboratory, it will be assessed for viability (e.g., enough stool, damaged collection kit, etc.). If the stool sample does not meet the predefined requirements, the CRO will be immediately notified using an online portal. The CRO will contact the subject to request another stool specimen. If collection can occur prior to the participant's colonoscopy appointment, a subsequent collection kit will be shipped to the participants residence. If a kit cannot be issued in time, the study member will offer to reschedule the colonoscopy for the participant. If the participant is unwilling to reschedule the colonoscopy or if the participant does not wish to provide a subsequent stool sample, the patient will be considered ineligible and will be withdrawn from the study.

Title: CRC-PREVENT Clinical Validation Protocol

**Document Number: VAL-PRT-0041** 

#### 5.3 Sample Assays

Samples will be shipped in the mail at ambient temperature for up to 4 days. Samples may be stored at -80 degrees C as eukaryotic cell fractions and as total extracted nucleic acid. Trained technicians at the laboratory will be blinded to results of the colonoscopy. Care will be taken to ensure that the proper unique patient identifier is associated with all results.

Samples will be assessed to ensure they are sufficient for testing. If the sample arrives in a condition that is insufficient for testing, the CRO will be notified and the issuance of a subsequent kit will be attempted. If this is not possible, the subject's data will be deemed unevaluable and will not be used in the analysis. Samples that fail quality assessment will be noted and assessed by the Sponsor.

For samples that are processed, the assay result for the mt-sRNA test will be "positive", "negative", or "no result". A "no result" will be reported if a step in the analytic process fails to meet the quality metrics of the manufacturer. This can occur based on a control failure, a failure of RNA quantification, a failure of the hemoglobin assessment, or other process failure. Samples with a "no result" label will not be included in the study analysis.

#### 5.4 Evaluation of a iFOBT test results

Once a collection kit is received by laboratory technologists at Geneoscopy, the iFOBT test will be evaluated using the iFOBT OC Auto® Micro 80 Analyzer. The output from this instrument is a continuous value, which indicates the concentration of hemoglobin in the stool sample. Geneoscopy will use a threshold value such that if the output from the iFOBT OC Auto® Micro 80 Analyzer is greater than the threshold, then the iFOBT test will be positive. If the output from the iFOBT OC Auto® Micro 80 Analyzer is less than the threshold, then the iFOBT test will be negative. The binary iFOBT result (positive or negative) is used as input into the mt-sRNA test software to determine the composite result for the diagnostic.

#### 5.5 Analysis of seRNA in stool samples

In parallel with the iFOBT test analysis, the stool sample will be processed. Specifically, the stool sample will be homogenized, and approximately 45 mL of the homogenate will be aliquoted into 50mL conical tubes. The homogenate will be subjected to differential centrifugation using a tabletop centrifuge and the supernatant will be discarded. The pellet will be lysed using a thiocyanate guanidine-based lysis buffer. The lysate will be subjected to further centrifugation and filtration to preferentially isolate the eukaryotic nucleic acids. The layer enriched with human nucleic acid is used for nucleic acid extraction (**Figure 1**).

[figure not shown]

Figure 1. Methods for manual human nucleic acid enrichment using differential centrifugation.

Total nucleic acid isolation will be performed on the purified seRNA using the bioMérieux EMAG as per the manufacturer's instructions. The output from the EMAG is subsequently exposed to DNase treatment for removal of DNA contaminants that impact assay expression. Subsequently, the solution is subjected to a cleanup protocol using the bioMérieux EMAG as per the manufacturer's instructions.

Titl	le:	CRO	C-P	RE'	VEI	NT

Clinical Validation Protocol

**Document Number: VAL-PRT-0041** 

Each sample will be evaluated for seRNA targets. The seRNA targets are quantified using Bio-Rad's QXDx ddPCR System (510(K) K181661). Evaluation of each seRNA biomarker requires use of a single assay, which consists of two primers and a fluorophore labeled probe. The probe can be labeled with FAM, HEX, or VIC. Assays can be duplexed such that two assays (four probes and two different fluorophores) are added to each well that is analyzed by the QXDx ddPCR system. The output from the QXDx system is a quantification of the concentration of all measured markers in the sample (Figure 2).

[figure not shown]

Figure 2. Methods for digital droplet PCR development and output for assessing quantification of human nucleic acid in purified RNA.

#### 5.6 Generation of a Test Result

The software component will store, query, and process the required features (iFOBT test result, demographics, and RNA quantification) to determine an output for each mt-sRNA test (positive, negative, or no result). Input data required for the software will be stored in an online cloud-based storage unit. Using the software, data will be queried and transformed to generate the input layer for assessment by the model. Pushing the data through the model will generate a composite score for each individual patient. This score is calculated by multiplying the patient's individual features (expression, demographic information, and stool hemoglobin assay (iFOBT) results) by a predetermined constant marker-specific weighting factor. The aggregate of these individually weighted marker results determines the composite score, whereby a higher output score indicates that the patient has a higher risk of having an advanced adenoma (AA) or colorectal cancer (CRC). The composite score will be compared to a predetermined threshold. If the composite score is above the predetermined threshold, then the result will be reported as positive. If the composite score is below the predetermined threshold, the result will be reported as negative. If a score cannot be computed for any reason, the software will report "no result". The final output from the software is a patient report that will indicate the result from the mt-sRNA test.

#### 5.7 Conducting a colonoscopy

After stool samples collection, the subject will undergo a routine, standard-of-care screening colonoscopy. The CRO will provide the subjects with reminders to attend their colonoscopy and to follow the instructions of their physician. Once the subject confirms the appointment, the participant will be instructed on how to prepare for a colonoscopy by the gastroenterologist at the endoscopy site. Consent and instructions for the colonoscopy procedure will also be provided by the endoscopy site. The night prior to the colonoscopy, the participant will prepare for the procedure according to the endoscopy site's instructions.

During the procedure, if the physician observes any findings, these findings will be reported, as per site-specific standard of practice. If lesions are removed during the procedure, the lesion will undergo histopathology review, as per normal practice of each clinical site. If the participant had no findings during the colonoscopy, the participant will not have associated histopathology.

Title: CRC-PREVENT Clinical Validation Protocol

**Document Number: VAL-PRT-0041** 

The endoscopist will record the quality of the colonoscopy procedure. Quality metrics will include bowel preparation, colonoscopy withdrawal time, and procedure completion. If the quality of the colonoscopy was limited in any way, but the endoscopist observed a colorectal cancer or an advanced adenoma, then the participant will be eligible for the study. If the quality of the colonoscopy was limited but the colonoscopist did not observed an advanced adenoma or a colorectal cancer, then the subject can be considered eligible for the study. If the participant does not wish to receive a subsequent colonoscopy or the participant does not meet the aforementioned criteria, then they will be deemed ineligible for the study. Poor quality can include:

- Poor bowel preparation is poor (i.e., large amounts of stool, <90% of surface could be examined, or lesions <5mm could not be observed),
- Incomplete colonoscopy (did not reach the cecum, or small / large intestinal junction, or neo-cecum)

During this process, the CRO will contact the subject to find out whether they attended their appointment and if they have any questions about their participation in the study. If it is learned that the appointment was not attended, the CRO will communicate with the subject about the need to reschedule and collect new appointment details in order to maintain eligibility. These communications will come in the form of texts, emails, and outbound calls.

#### 5.8 Obtaining clinical information, demographics and identification

Copies of subjects' medical records related to their colonoscopy are required to conclude participation in this study. Medical Record Release Forms will be signed during enrollment via a secure signature platform. Subjects will complete a medical record release form for each doctor involved in the recommendation and completion of their routine, standard-of-care, screening colonoscopy visit. Completed Medical Record Release Forms will be used by the study team to proactively request necessary records from each doctor involved in the recommendation and completion of the subject's routine, standard-of-care, screening colonoscopy.

Medical records may be obtained from the participant's primary care physician, the gastroenterologist who performed the procedure, and/or the pathologist who reviewed tissue extracted during the endoscopy. Medical records may include the following:

#### Primary Care Physician Medical Records

- o Participant Name
- o Participant Date of Birth
- Gender
- o Sex
- o Age
- Ethnic Background
- Smoking Status
- Pathology Center Information
- Treating Physician Information
- Date of procedures
- o Prescriptions
- History and Physical Information

## Gastroenterologist Medical Records

Participant Name

Title: CRC-PREVENT Clinical Validation Protocol

**Document Number: VAL-PRT-0041** 

- o Participant Date of Birth
- o Gender
- o Sex
- o Age
- Ethnic Background
- Smoking Status
- o Endoscopy Center Information
- Treating Physician Information
- Colonoscopy Date
- Colonoscopy Time
- o History and Physical Information
- o Number of Lesions Removed
- Location of Lesions

#### Pathology Medical Records

- o Participant Name
- o Participant Date of Birth
- Gender
- Sex
- o Age
- Ethnic Background
- Smoking Status
- History and Physical Information
- Pathology Center Information
- Treating Physician Information
- o Number of lesions reviewed
- Lesion Category
- Lesion Size
- Recommended Clinical Care

Records will be sent to study members at the CRO via a secure method (secure FAX, secure email, or mail). All members at the CRO are non-conflicted study members. Medical records will be reviewed by study members at the CRO prior to uploading to the CRO's centralized database. Subsequently, the data will be reviewed by internal pathologists that are contracted by the CRO. All pathologists are non-conflicted study members. The pathologists will record information about the colonoscopy and the histopathology to determine disease severity (**Table 1**). These data will be entered into the CRO's centralized database. Each record will be linked to a participant using a unique patient identifier (UPN). All subsequent data obtained or distributed will be linked to the UPN. All data will be subject to a Data Management Plan.

#### 5.9 Categorization of patients based on colonoscopy / histopathology

The results from the colonoscopy and histopathology will be blinded to study members at Geneoscopy. These results will be obtained and stored by a non-conflicted entityin a secure and HIPAA compliant portal.

Title: CRC-PREVENT Clinical Validation Protocol

**Document Number: VAL-PRT-0041** 

The entity will generate patient labels based on colonoscopy findings and subsequent histopathology, if applicable. Patient classifications will be performed based on a pathology review standard operating procedure (SOP) that is aligned with the College of American Pathologists Protocol for Examination of Excisional Biopsy Specimens From Patients With Primary Carcinoma of the Colon and Rectum version 4.1.0.0. Initially, pathologists will report the number of lesions identified on a colonoscopy and the colonoscopy quality. The number of lesions will be an integer and can include 0. If there were no lesions observed on a colonoscopy, the entry will be considered complete. If lesions were identified on a colonoscopy, for each lesion, classification will require evaluating lesion location within the colon (site), specimen integrity, size (mm), configuration, and histology. Colon site can include: cecum, ileocecal valve, ascending colon, hepatic flexure, transverse colon, splenic flexure, descending colon, sigmoid colon, rectosigmoid colon, rectum, other (specify), not specified. Specimen integrity can include: intact, fragmented, or not specified. Polyp size will be reported as an integer in millimeters. The polyp size will be derived from the colonoscopy report. If the colonoscopy report provides a value that is a range, the average value of the range will be reported. If the colonoscopy report provides a value that is descriptive (i.e., diminutive, or small), the size will be reported according to the pathology reporting SOP. Polyp configuration will be reported as pedunculated, sessile, or not specified. Histology will be reported as one of the following: carcinoma, carcinoma in-situ, adenoma with high-grade dysplasia, tubular adenoma, villous adenoma, tubulovillous adenoma, traditional serrated adenoma, sessile serrated adenoma, sessile serrated polyp, hyperplastic polyp, fecal matter, normal mucosa, lymphoid aggregate, hamartomatous polyp, lipoma, neuroendocrine tumor, sarcoma, lymphoma, or other. After information has been submitted for each lesion, the pathology review will be considered complete.

Pathology review will be performed by two independent reviewers and will be compared for consistency using an internal algorithm. If inconsistencies exist, a third reviewer will provide classification information and the third review will be compared to the two original reviews. If the third review agrees with one of the original reviews, this will be the ultimate pathology review for the patient. If all three reviewers disagree with the label, the principal investigator on the study will evaluate all information and generate a final review of the patient.

Once pathology reviews are finalized, patient categories will be generated based on the information provided in **Table 1**. Subjects will be categorized by the most clinically significant lesion. Lesion categories from highest severity to lowest severity include colorectal cancer, advanced adenomas, other precancerous adenomas, hyperplastic polyps, and then no findings on a colonoscopy. Patients with invasive carcinoma will be classified as Category 1. Patients with an advanced adenoma will be classified as Category 2. Patients with other non-advanced adenomas will be classified as Category 3-5. Patients with hyperplastic polyps or with no findings on a colonoscopy will be classified as Category 6. Subcategories will also be determined using **Table 1** based on number of lesions, lesion size, and histology. For patients with CRC, additional reports will be obtained to assist in CRC staging. For all CRCs, lesion location, size, and TNM stage will be determined and recorded.

If the participant does not have a cancer or an advanced adenoma and the colonoscopy and histopathology reports are not clear enough to generate a definitive pathology classification, the participant will be excluded from the study analysis. Reasons for this type of exclusion can include: a biopsy or excision was not performed, the specimen was lost or mislabeled, the specimen was destroyed during the excision process, traceability between the colonoscopy lesion and the histopathology reading is not maintained, or other circumstance where pathology classification is not possible.

Based on the colonoscopy and histopathology results, patient management will be completed by physicians at the endoscopy center. Results from the mt-sRNA test will not be provided to patients.

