**Document Number: VAL-PRT-0041** 

histopathology will be blinded to laboratory technologists at Geneoscopy. To assess the accuracy profile, colonoscopy results will be stored by a second clinical research organization (CRO). Ultimately, Geneoscopy study members will supply the CRO with mt-sRNA test results. Study members at the CRO will link mt-sRNA test results to colonoscopy results to assess the primary endpoints of this study.

Table 1. Histopathological category definitions

Category	Binary Category	Description
Colorectal Cancer (CRC)	Positive	Stage I-IV colorectal cancer, any size
Advanced Adenomas (AA)	Positive	High-grade dysplasia or ≥10 adenomas, any size Tubulovillous adenoma, any size Tubular adenoma, ≥10mm Traditional serrated adenoma, ≥10mm
Medium Risk Adenomas (MRA)	Negative	Hyperplastic polyp or SSL, ≥10mm 5-9 adenomas (TA + SSL), <10mm 3-4 adenomas (TA + SSL), <10mm
Low Risk Adenomas (LRA)	Negative	1-2 adenomas (TA + SSL), 5-9mm 1-2 adenomas (TA + SSL), <5mm
No Findings (NEG)	Negative	Hyperplastic polyps, <10mm Benign lesions, any size No lesions on colonoscopy

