**Document Number: CT-PLN-0002** 

| Insurance No Insurance Private Insurance Public Insurance (Medicaid) Public Insurance (Medicare Advantage) Public Insurance (Medicare) Self-Insured | x (xx) |
|---|--------|--------|--------|--------|--------|--------|
| Geographic
Rural
Urban / Suburban   | x (xx) |

Table 6. Data summaries for subject categories will be generated for sensitivity and specificity

Category	Label	True Outcome	Colonoscopy Findings	% (N)
1	Colorectal Cancer	Positive	Stage I-IV colorectal cancer, any size	x (xx)
2	Advanced adenoma	Positive	High-grade dysplasia or ≥10 adenomas, any size Tubulovillous adenoma, any size Tubular adenoma, ≥10mm Traditional serrated adenoma, any size	x (xx)
3	Other adenoma	Negative	Hyperplastic polyp or SSL, ≥10mm 5-9 adenomas (TA + SSL), <10mm 3-4 adenomas (TA + SSL), <10mm	x (xx)
4	Other adenoma	Negative	1-2 adenomas (TA + SSL), 5-9mm 1-2 adenomas (TA + SSL), <5mm	x (xx)
5	Negative	Negative	Hyperplastic polyps, <10mm Benign lesions, any size No lesions on colonoscopy	x (xx)

**Table 7.** Data summaries for all subjects will be summarized in a frequency table:

	Ti
GENEOSCOPY, INC.	D

**Fitle:** CRC-PREVENT Statistical Analysis Plan

**Document Number:** CT-PLN-0002

Mt-sRNA Test Result		Histopathological Lesion Category Grouping						
	CRC (1) % (n)	AA (2) % (n)	OA (3) % (n)	OA (4) % (n)	NEG (5) % (n)	Total		
Positive	a	b	С	d	e	a+b+c+d+e		
Negative	f	g	h	i	j	f+g+h+i+j		
Total	a+f	b+g	c+h	d+i	e+j	N		

The primary endpoint metrics will be calculated as:

- Mt-sRNA test sensitivity for subjects with CRC = a / (a+f)
- Mt-sRNA test sensitivity for subjects with AA = b / (b+g)
- Mt-sRNA test specificity for subjects with negative findings = j / (e+j)

For each of these metrics, the two-sided 95% exact binomial confidence intervals will be provided, and the lower 95% confidence limits will be compared to the acceptance criterion. An additional sensitivity calculation will be presented for subjects with Other Adenomas.

- Mt-sRNA test sensitivity for subjects with OA(3) = c/(c+h)
- Mt-sRNA test sensitivity for subjects with OA(4) = d/(d+i)

The two-sided 95% confidence interval will be calculated for this metric although there is no specific acceptance criterion against which it will be compared.

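### Averaging a size range that covers several polyps can place a subject with a reported tubular adenoma of 10 mm or more below the advanced-adenoma category

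*Protocol*

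**What the plan says.** Protocol Section 5.9 fixes lesion size in three sentences. On source: "The polyp size will be derived from the colonoscopy report". On precision: "Polyp size will be reported as an integer in millimeters". On ranges: "If the colonoscopy report provides a value that is a range, the average value of the range will be reported". Descriptive sizes such as small or diminutive are referred to a pathology reporting SOP; ranges are not.

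The same section sets the subject label: "Subjects will be categorized by the most clinically significant lesion". Two reviewers classify independently, and a third is called only if their reviews differ.

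In Table 1 (Protocol Section 1.2; SAP Section 4.2) the size-dependent AA entries are "Tubular adenoma, ≥10mm Traditional serrated adenoma, ≥10mm". High-grade dysplasia, tubulovillous adenoma and 10 or more adenomas are AA at any size. Smaller tubular adenomas are medium risk (MRA) or low risk (LRA) by number and size. Hyperplastic polyps are MRA from 10 mm and negative (NEG) below it. SAP Table 6 differs on one entry: "Traditional serrated adenoma, any size".

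SAP Section 9.1 estimates AA sensitivity as b/(b+g) over subjects labelled AA, and specificity as j/(e+j) over NEG only. AA success needs an estimate above 45% and a lower 95% limit above 40% (SAP Section 4.2.1).

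**The concern.** A range in a colonoscopy report can mean two things: uncertainty about one lesion, or the spread from the smallest to the largest of several polyps. The averaging rule suits the first. Applied to the second, it discards the one size that decides the subject's label.

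The Protocol synopsis expects over 6,000 endoscopy sites, and Section 5.7 leaves the reporting of findings to each site's practice, so nothing visible in the plan prevents grouped reporting. Section 5.8 lists lesion size among the pathology records, but Section 5.9 takes size from the colonoscopy report.

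At stake are the membership of the AA co-primary denominator, the membership of the specificity denominator through hyperplastic polyps, and the secondary serrated-lesion endpoint. The double review offers little protection: two reviewers who apply the same written rule agree, so the third review is not called.

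**Working it through.** The plan gives no figure on this point. Its one probability, a 68% chance of at least 48 cancers among 8,500 subjects at 0.6% prevalence, reproduces (exact binomial tail 68.2%) but has no bearing here. The check is therefore of the rule itself: recorded size = (low + high)/2, compared with 10 mm.

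**1. One range, several polyps of the same histology**
- Three tubular adenomas, 4 to 12 mm: (4 + 12)/2 = 8 mm. Averaging gives 3-4 adenomas under 10 mm, hence MRA. Labelling by the most significant lesion gives a 12 mm tubular adenoma, hence AA.
- Direction: the average never exceeds the upper end. If it reaches 10 mm, the largest polyp does too, and the AA label is right. If it falls short while the upper end is 10 mm or more, the label is too low. At this cut the rule can demote but cannot wrongly promote.
- Hyperplastic polyps, 4 to 12 mm: the average is again 8 mm. The subject moves from MRA to NEG, enters j/(e+j), and leaves the serrated endpoint, read as lesions of 10 mm or more.

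**2. One lesion, range straddling 10 mm**
- 8-10 gives 9 and 5-12 gives 8.5: below the cut.
- 8-12, 9-11 and 5-15 give 10: AA, although the lesion may be smaller.
- 9-10 and 4-15 give 9.5. Size must be an integer and no rounding rule is stated, so rounding decides the label.
- Over integer ranges with low end 5-9 and high end 10-15 (30 ranges), 10 fall clearly below the cut, 5 land on 9.5, and 15 are at 10 mm or more. The grid shows that both directions occur; it does not show how often.
- A range lying wholly at 10 mm or more never averages below 10.

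**3. What a shift could do to AA sensitivity**

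All inputs here are assumptions: 600 true AA subjects and a fraction m moved out. Sensitivity after a one-way loss = (600·s − 600·m·s_out)/(600 − 600·m), where s is overall sensitivity and s_out is sensitivity in those moved out.

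| s | s_out | m | Result |
|---|---|---|---|
| 46% | 30% | 2% | (276 − 3.6)/588 = 46.3% |
| 46% | 30% | 5% | (276 − 9)/570 = 46.8% |
| 46% | 30% | 10% | (276 − 18)/540 = 47.8% |
| 46% | 46% | any | 46.0% |
| 44% | 25% | 5% | (264 − 7.5)/570 = 45.0% |

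If 30 subjects leave (s = 46%, s_out = 30%) and 30 smaller-lesion subjects with an assumed 22% positive rate enter, the result is (276 − 9 + 6.6)/600 = 45.6%, below the starting 46.0%. One-way loss applies to the grouped case; two-way exchange applies to single-lesion ranges.

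**The case against.** The strongest reply is that Section 5.9 asks for size lesion by lesion and speaks of a value that is a range, which most naturally means one lesion of uncertain size. A reviewer who also keeps the most-significant-lesion rule in mind could code the largest polyp at 12 mm. Two reviewers might differ and so trigger the third review. The pathology review SOP, which is not among the documents, may settle grouped ranges and rounding.

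Part of this stands. The grouped reading is not compelled, and the SOP may help. But the range sentence carries no limit to single lesions, and it sits beside a sentence that does hand descriptive sizes to an SOP. The route that excludes subjects with unclear reports applies when classification is not possible. Here the averaging rule supplies a classification, so that route need not open.

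A reader might infer that the rule removes true AA subjects overall, in one direction. The documents do not support that: for a single lesion with a straddling range the true size is unknown, and the rule also moves lesions up.

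A reader might also apply the feasibility hold-out's AA share (50/366 = 13.7%) to the 8,500 and assume that a few percent are reported as ranges. The few percent has no source, the 8,500 are recruited rather than evaluable, and the share may include AA that does not depend on size. A count built that way is not evidence.

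**Conclusion.** The point holds for one range that covers several polyps of the same histology. There the written rule can give a label that contradicts both Table 1 and the instruction to label by the most significant lesion. The error at the 10 mm cut is one-directional: tubular adenoma moves from AA to MRA or LRA. Hyperplastic polyps move from MRA to NEG, which does alter the specificity denominator; subjects moved from AA to MRA or LRA do not enter it. High-grade dysplasia, tubulovillous adenoma and 10 or more adenomas are untouched. Traditional serrated adenoma is affected under Table 1 but not under SAP Table 6, and those two entries must be reconciled.

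The rounding gap at 9.5 mm is real for any range.

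The size of the effect cannot be computed, because the documents give neither the frequency of ranges nor test performance in the subjects concerned. The illustrations show that the AA estimate could rise, stay the same or fall. In one assumed case it rises from 44.0% to the 45% threshold, which success requires it to exceed. A reader should not conclude that the AA result is inflated or that any success decision would change; neither is shown.

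**What to change.** In Protocol Section 5.9 and the pathology review SOP:

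- Limit averaging to a range given for a single lesion, and state how 9.5 mm is rounded.
- Where a range covers several lesions of the same histology, assign its upper limit to the largest lesion and apply Table 1 to that.
- Where histology is mixed and the largest lesion cannot be linked to its histology, do not assign the upper limit to an adenoma by default. Send the record to the existing tie-break or unclear-classification route.
- Re-code range-sized records before the colonoscopy dataset is locked, with reviewers still blinded to test results.
- Add to the SAP a sensitivity analysis of AA sensitivity with straddling ranges classified once by the upper end and once by the lower end.

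The cost is a few sentences and some blinded re-review of existing reports. Section 5.9 stores an integer and mentions no flag for sizes taken from a range, so finding these records may mean reopening reports. SAP Section 7.1 describes enrolment as running through June 2022 with about 14,000 consented, so this work should be scheduled ahead of lock. If lock has already taken place, the sensitivity analysis is what remains.
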